8.5.2. Sensitivity Analyses of the Primary Efficacy Endpoint

Robustness of the primary analysis of the primary efficacy endpoint due to missing data or premature treatment discontinuations (including the impact of COVID-19) will be explored by the following sensitivity analyses:

- Mixed-effects model (as described in [Section 8.5.1.1](#) and Section 8.5.1.2) with multiple imputation
- Tipping point approach of the multiple imputation analysis, as described in [Section 6.6.1.2.2](#)

- Mixed-effects model (as described in [Section 8.5.1.1](#) and [Section 8.5.1.2](#)) using treatment completers only (patients who completed blinded treatment)
- Mixed-effects model (as described in [Section 8.5.1.1](#) and [Section 8.5.1.2](#)) including local lab data

To assess the robustness of choice of change point, the primary efficacy analysis of eGFR chronic slope over 2 years will be repeated using a different change point at Week 4 and Week 8.

To assess the impact of changes in immunosuppressive medications, the primary efficacy analysis will be repeated by excluding assessments after initiation or intensification of immunosuppressive medication in the blinded treatment period.

To assess the potential impact of patient evaluability and major protocol deviations, the primary efficacy analysis will be repeated using the PP Analysis Set.

8.6. Analysis of the Surrogate Efficacy Endpoint

8.6.1. Primary Analysis

The primary analysis of the surrogate endpoint will be based on the IAS. The proportion of patients achieving FPPE, defined as UP/C ≤ 1.5 g/g (170 mg/mmol) and a $>40\%$ reduction from baseline, will be analyzed using a generalized linear model with logit link function (using SAS PROC GENMOD) to model the probability of achieving FPPE. The response variable will be FPPE outcome through Week 60 (ie, only FPPE results through Week 60 will be included in the model). Missing response variables will be imputed using the MI procedure prior to analysis (see [Section 6.6.2.1](#)). Fixed effects in the model will include baseline UP/C (natural log), treatment, time (categorical, in weeks), and treatment by time interaction. Analysis will be stratified by randomization stratification variable (4 levels based on Screening eGFR and UP/C). An unstructured covariance matrix within subject will be assumed. If convergence issues arise, the autoregressive-1 covariance structure will be used.

The probability of achieving FPPE at Week 36 (risk) for each treatment group, treatment effect at Week 36 (risk difference), standard errors of risk and risk difference, 95% CIs of risks and risk difference, and p-values will be extracted from the model. Relative risk ratios and odds ratios, along with 95% CIs, will also be presented. Relative risk will be obtained from the same model described above with the exception that a Poisson distribution with log link function will be used.

The primary analysis described above will also be performed using the FAS population at the final analysis using all data through Week 108.

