4.3.1.1. Surrogate Endpoint: FPPE

Based on the results at Week 8 of the sparsentan Phase 2 DUET study (RET-D-001) in FSGS patients and projected to Week 36, it is assumed that sparsentan will result in approximately 50% of patients achieving FPPE, and that irbesartan will result in approximately 20% of patients achieving FPPE. Based on these assumptions and using a Pearson chi-square test for 2 proportions and a 2-sided α level of 0.05, 190 patients (approximately 95 per treatment group) will yield at least 90% power to detect a difference in response proportions between sparsentan and irbesartan. The minimum treatment difference that could be declared statistically significant is approximately 13% with approximately 190 patients.

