8. EFFICACY

8.1. General Considerations

All efficacy analyses will be based on the FAS or IAS, as described below. The primary, surrogate, and secondary endpoint analyses will also be performed on the PP Analysis Set as supportive analyses. All primary efficacy analyses based on laboratory data will use central lab data only. All efficacy analyses specified below refer to the double-blind period only.

UP/C will be determined using first morning void urine samples and will be calculated as the geometric mean of 3 first morning void urine samples collected within 5 days prior to the visit. If one of the samples is missing, the average of the other 2 samples will be used. As UP/C is a highly right-skewed variable, analyses will be performed on log-transformed data. For ease of interpretation, results will be presented in the original units.

The eGFR for each baseline and post-baseline visit will be determined using the CKD-EPI (Levey 2009) formula for patients ≥ 16 years of age at the time of screening and the Modified Schwartz formula for patients < 16 years of age at the time of screening (Schwartz 2009a; Schwartz 2009b).

For the purposes of efficacy analyses, an assessment is considered “on treatment” if it occurs after the first dose of study medication and no more than 3 days after the date of last dose of randomized treatment.

For all least-squares (LS) means that include strata coefficients, the observed strata proportions will be used instead of assuming equal sizes of strata.

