8.2. Statement of the Null and Alternative Hypotheses

The final analysis of the primary endpoint in non-US countries will test the following hypothesis using the FAS:

- H_0 : Slope of eGFR over the blinded treatment period (after adjusting for early hemodynamic effects) is equal between sparsentan and irbesartan
- H_1 : Slope of eGFR over the blinded treatment period (after adjusting for early hemodynamic effects) is different between sparsentan and irbesartan

The final analysis of the primary endpoint in the US will test the following hypothesis using the FAS:

- H_0 : Slope of eGFR over the blinded treatment period is equal between sparsentan and irbesartan
- H_1 : Slope of eGFR over the blinded treatment period is different between sparsentan and irbesartan

The interim analysis of the surrogate endpoint at Week 36 will test the following hypothesis using the IAS:

- H_0 : Proportion of patients achieving FPPE at Week 36 is equal between sparsentan and irbesartan

- H₁: Proportion of patients achieving FPRE at Week 36 is different between sparsentan and irbesartan

The final analysis of secondary efficacy endpoints in non-US countries will test the following hypotheses using the FAS:

- H₀₁: Percent change from Week 6 in eGFR at Week 108 is equal between sparsentan and irbesartan
- H₁₁: Percent change from Week 6 in eGFR at Week 108 is different between sparsentan and irbesartan
- H₀₂: Percent change in eGFR from baseline to 4 weeks post-cessation of randomized treatment at Week 112 is equal between sparsentan and irbesartan
- H₁₂: Percent change in eGFR from baseline to 4 weeks post-cessation of randomized treatment at Week 112 is different between sparsentan and irbesartan
- H₀₃: Slope of eGFR over the blinded treatment period is equal between sparsentan and irbesartan
- H₁₃: Slope of eGFR over the blinded treatment period is different between sparsentan and irbesartan

The final analysis of secondary efficacy endpoints in the US will test the following hypotheses using the FAS:

- H₀₁: Slope of eGFR over the blinded treatment period (after adjusting for early hemodynamic effects) is equal between sparsentan and irbesartan
- H₁₁: Slope of eGFR over the blinded treatment period (after adjusting for early hemodynamic effects) is different between sparsentan and irbesartan
- H₀₂: Change in eGFR from baseline to 4 weeks post-cessation of randomized treatment at Week 112 is equal between sparsentan and irbesartan

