8.8.2. UP/C Endpoints

8.8.2.1. Proportion of Patients Achieving FPPE

For the analysis of the proportion of patients achieving FPPE, defined as UP/C ≤ 1.5 g/g (170 mg/mmol) and a $>40\%$ reduction from baseline, the by-visit estimates from the model described in [Section 8.6.1](#) will be utilized. Analysis will be performed using IAS at interim analysis and FAS at final analysis. At interim analysis, only FPPE results through Week 60 will be included. LS means for the probability of achieving FPPE (risk) for each treatment group and treatment effect (risk difference) at each visit will be extracted from the model. Relative risk ratio and odds ratio will also be presented.

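### The Week 36 surrogate risks and risk difference are planned as LS means from a covariate-adjusted logit model, which are not the proportions of patients named in the hypothesis

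*SAP*

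**What the plan says.** SAP 8.2 gives the surrogate null hypothesis as "Proportion of patients achieving FPPE at Week 36 is equal between sparsentan and irbesartan".

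SAP 8.6.1 fits a logit model in the IAS with log baseline UP/C, treatment, visit, treatment by visit and the four-level randomization stratum. From it are taken the Week 36 risks and the "treatment effect at Week 36 (risk difference), standard errors of risk and risk difference, 95% CIs of risks and risk difference". That section, like Protocol 12.7.1.2, says only that these quantities come from the model.

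SAP 8.8.2.1 uses the by-visit estimates of the same model and says what they are: "LS means for the probability of achieving" the response, by treatment group, with the risk difference. SAP 8.1 adds that, for LS means that include strata coefficients, "the observed strata proportions will be used instead of assuming equal sizes of strata". Neither document says that predicted probabilities are averaged over patients.

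For the ratio, SAP 8.6.1 states: "Relative risk will be obtained from the same model described above", but with a Poisson distribution and a log link.

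The planning figures in SAP 4.3.1.1 are in proportions of patients. For sparsentan, "it is assumed that sparsentan will result in approximately 50% of patients achieving FPPE", against 20% on irbesartan. The calculation is made "using a Pearson chi-square test for 2 proportions and a 2-sided α level of 0.05", and "190 patients (approximately 95 per treatment group) will yield at least 90% power".

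**The concern.** An LS mean from a logit model is formed on the linear predictor at average covariate values and then back-transformed. The inverse logit of an average is not the average of the inverse logits, so the result is the probability for one notional patient and not the share of patients who respond. Weighting strata by their observed proportions does not cure this, because the weights also act on the linear predictor. Nor does the repeated-measures covariance structure, which deals with correlation between visits and not with averaging over baseline covariates.

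The gap exists only if the covariates are prognostic. Here that is close to built in: response requires UP/C at or below an absolute limit of 1.5 g/g, and entry requires at least 1.5 g/g (Protocol 7.1.1), so patients who start higher have further to fall.

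At stake is the accuracy of the main interim result: two reported risks and a difference that do not estimate the quantities in the hypothesis, shown beside a relative risk that does not equal their ratio.

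**Working it through.** **1. The plan's own figures.** Inputs from SAP 4.3.1.1: 0.50 vs 0.20, 95 per arm, two-sided 0.05.

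- Pooled SE: √(2 × 0.35 × 0.65 / 95) = 0.0692. Unpooled SE: √((0.25 + 0.16) / 95) = 0.0657.
- Power: Φ((0.30 − 1.96 × 0.0692) / 0.0657) = Φ(2.50) = 99.4%, consistent with at least 90%.
- Minimum significant difference: 1.96 × 0.0657 = 12.9%, or 12.5% with a pooled SE at a 20% control rate. Both match the stated 13% or so.

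These figures rest on a chi-square test of proportions and do not depend on how the model risks are formed.

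**2. Size of the gap.** Let s be the SD of the covariate part of the logit. It is not in the documents, so it is an assumption and is varied. For a true proportion p, solve E[expit(η + sZ)] = p for η, with Z standard normal. The LS mean is expit(η). For small s the understatement is about ½ s² p(1 − p)(1 − 2p).

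As a check at p = 0.20 and s = 0.5: ½ × 0.25 × 0.20 × 0.80 × 0.60 = 0.012, which gives 0.188 (exact 0.189). At p = 0.50 the term is zero.

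| True rates | s | LS mean, sparsentan | LS mean, irbesartan | LS-mean difference | True difference |
|---|---|---|---|---|---|
| 0.50 / 0.20 | 0.5 | 0.500 | 0.189 | 0.311 | 0.300 |
| 0.50 / 0.20 | 0.75 | 0.500 | 0.176 | 0.324 | 0.300 |
| 0.50 / 0.20 | 1.0 | 0.500 | 0.161 | 0.339 | 0.300 |
| 0.281 / 0.094 | 0.5 | 0.271 | 0.086 | 0.185 | 0.187 |
| 0.281 / 0.094 | 1.0 | 0.245 | 0.067 | 0.178 | 0.187 |
| 0.33 / 0.20 | 1.0 | 0.299 | 0.161 | 0.138 | 0.130 |
| 0.20 / 0.20 | 1.0 | 0.161 | 0.161 | 0.000 | 0.000 |

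The second pair of rates is the Phase 2 Week 8 result in Protocol Section 4. The sign changes because the understatement is largest near p = 0.21 and shrinks on either side. At 50/20 almost all of it falls on the control arm. At 28.1/9.4 more of it falls on the sparsentan arm. With equal rates the difference is zero.

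**3. Simulated UP/C data.** Assumptions: lognormal screening UP/C truncated at 1.5 g/g, with median before truncation 2.5 or 3.5 g/g and log SD 0.4 or 0.6; baseline equal to screening plus log noise of SD 0.25; log change of SD 0.6, 0.8 or 1.0. Each of the twelve settings was calibrated to about 50% and 20% response on the trial's definition. The logit fit used treatment, log baseline UP/C and four strata.

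- The implied s was 0.40 to 1.20.
- The control LS mean was 0.147 to 0.193, and the LS-mean difference 0.308 to 0.348.
- The standardised difference (predicted probabilities averaged over patients) was 0.298 to 0.303, against observed differences of 0.298 to 0.302.

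At the Phase 2 Week 8 rates, one such setting gave LS means of 0.254 and 0.076 (difference 0.178), while standardisation returned 0.281, 0.094 and 0.187. A range of assumed spreads gave LS-mean differences of 0.169 to 0.183.

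**4. Relative risk.** In simulated data at 50/20 the Poisson log-link model returned 2.49 to 2.50, in line with 0.50 / 0.20 = 2.5. The ratio of the LS-mean risks in the table is 0.500 / 0.189 = 2.65 at s = 0.5 and 0.500 / 0.161 = 3.11 at s = 1.0.

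**The case against.** The strongest reply is that SAP 8.6.1 does not say that the risks are formed at mean covariates. The term LS means is attached to them in 8.8.2.1, an exploratory section, and a risk difference with a CI needs a step beyond a logit contrast that the SAP leaves open. Standardisation may have been intended. That stands in part: if it was intended, one sentence settles the point. But 8.8.2.1 describes estimates from the 8.6.1 model itself, and the only averaging rule given (8.1) is for LS means. On the text as it is, LS means are the plan.

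Second, patient-level percentages are already planned: the Week 36 Cochran-Mantel-Haenszel analysis (SAP 6.6.2.2 and 8.6.2) defines the percentage of responders. That helps a reader. It uses a different population and non-responder imputation, however, and the text does not say that it yields a risk difference.

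Third, the size rests on assumed spreads and on a single-visit fit, whereas the planned model is longitudinal and multiply imputed. That stands. The range is illustrative, and at the mild end the shift is about 1 point.

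A reader might infer more than the documents support:

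- *That the difference is always overstated.* It is not. The direction depends on the true rates and reverses at the Phase 2 Week 8 rates.
- *That the error carries into the projected eGFR benefit.* SAP 4.3.1.2 applies the 8.4 multiplier to the assumed 30% difference (0.30 × 8.4 = 2.52) for planning. No section schedules multiplying the estimated Week 36 difference by it, and the slope is estimated directly at the final analysis.
- *That the Poisson relative risk is wrong.* It targets the ratio of patient proportions. The mismatch comes from the LS-mean risks.

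**Conclusion.** The point holds as one of estimation and reporting. As written, the reported Week 36 risks are those of a patient at average covariates and not the proportions in the hypothesis. If baseline UP/C is prognostic, rates below 50% are understated. The risk difference is overstated by about 1 to 5 points at the planning rates and understated by up to about 2 points at the Phase 2 Week 8 rates. Both sizes rest on assumed UP/C spreads.

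It would be wrong to conclude that the interim gate is compromised. With equal rates the LS-mean difference is zero, the logit-scale test is the same however the risks are averaged, and the planned power was derived from proportions. The change should be made because it is cheap and gives the quantity that the SAP names, not because the test is unsound.

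**What to change.** Keep the 8.6.1 model and take the test from the Week 36 treatment contrast on the logit scale. For the reported estimates, within each imputed data set:

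1. Predict every IAS patient's Week 36 probability under sparsentan and again under irbesartan, and average each set over all patients.
2. Take the risk difference from these two standardised risks and, for consistency, the relative risk as well.
3. Obtain standard errors by the delta method or bootstrap, and combine across imputations by Rubin's rules.

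Align 8.8.2.1 with this wording, and apply the same rule to the repeat of the analysis in the FAS at the final analysis.

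The cost is a few sentences in the SAP and a little extra programming. The reported difference may be slightly smaller than the LS-mean version if the true rates are near 50% and 20%.

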8.6.2. Sensitivity Analyses of the Surrogate Efficacy Results

Robustness of primary analysis of the surrogate endpoint due to missing data and premature discontinuations (including COVID-19) will be explored by the following sensitivity analyses:

- CMH test, adjusting for the 2 randomization stratification factors to compare sparsentan with irbesartan, using Week 36 results only (without imputation), based on the same population used in the analysis per [Section 7.7](#). Only patients who would have been expected to have completed Week 36 based on the date of first dose will be

included; that is, subjects who discontinue prior to Week 36 but would have been expected to have completed Week 36 will be included. Patients with missing data at Week 36 will be considered non-responders. This sensitivity analysis was the originally planned primary analysis.

- CMH test with inclusion of UP/C assessments from a single urine sample
- Tipping point approach of the multiple imputation analysis as described in [Section 6.6.1.2.2](#)
- Observed cases analyzed using the primary model generalized linear model (no imputation)
- Inclusion of local lab data with central lab data analyzed using the primary model generalized linear model (no imputation)

To assess the potential impact of patient evaluability and major protocol deviations, the primary efficacy analysis will be repeated using the PP Analysis Set.

8.7. Analysis of the Secondary Efficacy Endpoints

8.7.1. Percent Change of eGFR from Week 6 to Week 108

The percent change of eGFR from Week 6 to Week 108 will be analyzed at the final analysis based on the FAS, using MMRM. The dependent variable will be all available on-treatment natural log(eGFR) data from Week 2 to Week 108. The model will include the following fixed effects:

- Treatment group (2 levels: sparsentan, irbesartan)
- Baseline eGFR in log scale
- Visit (categorical)
- Treatment group by visit interaction
- Randomization stratification variable (4 levels based on Screening eGFR and total urine protein)

In addition, patient will be included as a random effect.

The model will utilize restricted maximum likelihood estimation with Kenward-Roger method used to compute the denominator degrees of freedom for tests of fixed effects. An unstructured covariance matrix will be assumed. If convergence issues arise, autoregressive-1 covariance structure will be used.

Statistical significance of the treatment effect at Week 108 will be assessed by comparing with the treatment effect at Week 6. The LS mean estimate from the MMRM model will be used to perform treatment group comparisons. Estimates and CIs will be converted to percentages via the following transformations:

$$[\exp(\text{least squares mean change from Week 6 in natural log(eGFR)}) - 1] \times 100$$

Robustness of the analysis due to missing data and premature treatment discontinuations will be explored by the following sensitivity analyses:

- MMRM using multiple imputation
- MMRM using treatment completers only (patients who completed blinded treatment)

To assess the impact of changes in immunosuppressive medications, the analysis will be repeated by excluding assessments after initiation or intensification of immunosuppressive medication in the blinded treatment period.

To assess the potential impact of patient evaluability and major protocol deviations, the analysis will be repeated using the PP Analysis Set.

8.7.2. Change in eGFR from Baseline to 4 Weeks Post-cessation of Randomized Treatment (Week 112)

The change from baseline to 4 weeks post-cessation of randomized treatment (Week 112) will be analyzed via an analysis of covariance (ANCOVA) model using the FAS at final analysis. Only subjects who completed the 108-week treatment period will be included. The dependent variable will be the eGFR at analysis visit Week 112, with treatment and baseline eGFR included as fixed effects. The analysis will be stratified by the randomization strata. The treatment effect will be the contrast between sparsentan and irbesartan LS means. The LS means, treatment effect estimate, 95% CI, and p-value will be presented.

Robustness of the analysis due to missing data and premature treatment discontinuations will be explored by assessing the change from baseline to 4 weeks post End of Treatment (EOT) analysis visit.

To assess the impact of changes in immunosuppressive medications, the analysis will be repeated by excluding assessments after initiation or intensification of immunosuppressive medication in the blinded treatment period.

To assess the potential impact of patient evaluability and major protocol deviations, the analysis will be repeated using the PP Analysis Set.

8.7.3. Percent Change in eGFR from Baseline to 4 Weeks Post-cessation of Randomized Treatment (Week 112)

The percent change from baseline to 4 weeks post-cessation of randomized treatment (Week 112) will be analyzed using the FAS at final analysis using an ANCOVA model analogous to the one described in Section 8.7.2, with the exception that the response variable and corresponding baseline will be in natural log scale. Only subjects who completed the 108-week treatment period will be included. Estimates and CIs will be converted to percentage via the following transformations:

$$[\exp(\text{least squares mean change from baseline in natural log(eGFR)}) - 1] \times 100$$

Robustness of the analysis due to missing data and premature treatment discontinuations will be explored by assessing the change from baseline to 4 weeks post EOT analysis visit.

To assess the impact of changes in immunosuppressive medications, the analysis will be repeated by excluding assessments after initiation or intensification of immunosuppressive medication in the blinded treatment period.

To assess the potential impact of patient evaluability and major protocol deviations, the analysis will be repeated using the PP Analysis Set.

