12.7.3. Additional Efficacy Analyses

For the analysis of eGFR absolute change from baseline by visit, a MMRM model will be fitted to the available eGFR data, incorporating all post-baseline visits at which eGFR was measured for each patient during the double-blind period. The model will include treatment, both stratification factors for randomization, baseline eGFR, visit (categorical), and visit-by-treatment interaction as fixed effects. In addition, patient will be included as a random effect.

The model will utilize REML estimation with Kenward-Roger method used to compute the denominator degrees of freedom for tests of fixed effects. An unstructured within-patient covariance structure will be assumed. If the model does not converge under the unstructured covariance matrix, the autoregressive-1 covariance structure will be used. The LS mean estimate for $\beta_{\text{WKj}*\text{treatment}}$ (ie, the treatment effect at the visit j of interest) from the MMRM model will be used to perform treatment group comparisons by visit.

For the analysis of eGFR percent change from baseline by visit, a MMRM approach analogous to the model described for the absolute change from baseline will be used, except that the

response variable will be natural log(eGFR) and corresponding baseline value natural log(baseline eGFR). The LS mean estimate for $\beta_{\text{WK}j^* \text{treatment}}$ (ie, the treatment effect at the visit j of interest) from the MMRM model will be used to perform treatment group comparisons by visit. Estimates and CIs will be converted to percentages via the following transformation:

$$[\exp(\text{LS mean change from baseline in natural log(eGFR)}) - 1] \times 100$$

For the analysis of eGFR percent change from Week 6 by visit, the estimates from the MMRM model used in the analysis of eGFR relative percent change from baseline by visit described above will be utilized. However, for this analysis, the statistical significance of the treatment difference at visit j (eg, Week 108 for the secondary endpoint) will be assessed by testing the following hypothesis:

$$H_0: (\beta_{\text{WK}j^* \text{treatment}} - \beta_{\text{WK}6^* \text{treatment}}) = 0, \text{ versus:}$$

$$H_1: (\beta_{\text{WK}j^* \text{treatment}} - \beta_{\text{WK}6^* \text{treatment}}) \neq 0,$$

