4. STUDY DESIGN

4.1. Summary of Study Design

This is a randomized, multicenter, double-blind, parallel, active-control study, with an open-label extension of up to 156 weeks, in patients with FSGS. Patients who meet inclusion criteria during screening and who are taking renin-angiotensin-aldosterone system (RAAS) inhibitors will undergo a 2-week washout period from these agents prior to randomization. Approximately 300 eligible patients will be randomized 1:1 to receive either sparsentan or an active control (irbesartan). Randomization will include stratification by screening eGFR and UP/C values. The strata will be as follow:

- eGFR strata:
 - ≥ 30 to < 60 mL/min/1.73 m² (all patients)
 - ≥ 60 mL/min/1.73 m² (all patients)
- UP/C strata:
 - ≤ 3.5 g/g (396 mg/mmol; patients ≥ 18 years of age) or ≤ 2 g/g (226 mg/mmol; patients < 18 years of age)
 - > 3.5 g/g (396 mg/mmol; patients ≥ 18 years of age) or > 2 g/g (226 mg/mmol; patients < 18 years of age)

Additional antihypertensive agents are allowed during the study to maintain blood pressure $\leq 130/80$ mmHg (patients ≥ 18 years of age) or \leq the 75th percentile (patients < 18 years of age), with the exception of those that inhibit the RAAS and endothelin systems.

Study visits in the double-blind period will be conducted at 2, 4, 6, 8, and 12 weeks after randomization and at 12-week intervals thereafter. Following the 108-week blinded treatment period, treatment with study medication will be discontinued. Patients will return to the clinical site for the final visit of the double-blind period 4 weeks after study medication has been discontinued.

Patients may be evaluated for eligibility in the open-label extension using values from the Week 108 visit (end of blinded treatment period) as screening assessments. Patients with an eGFR < 30 (but > 20) mL/min/1.73 m² will be eligible for participation in the open-label extension at the discretion of the Investigator but will require close monitoring of eGFR and serum potassium.

Open-label extension study visits will be conducted at 12-week intervals. A study visit 2 weeks after the start of the open-label extension will also be conducted to assess tolerability to sparsentan.

Patients will participate in the open-label extension for up to 156 weeks, for a total of 268 weeks in the study (ie, double-blind and open-label periods).

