8.4. Multiple Comparisons and Multiplicity

The overall family-wise Type I error rate will be controlled by a hierarchical (gatekeeping) testing procedure.

The surrogate efficacy endpoint (UP/C response at Week 36) will first be tested at the interim analysis at 2-sided $\alpha = 0.05$. If the test is not significant, hypothesis testing stops. If the test is significant, then the following country-specific hierarchical testing will be performed.

For non-US countries, the hierarchy for the hypothesis testing will be as follows, if the test of the surrogate efficacy endpoint (UP/C response at Week 36) is significant:

1. test the primary efficacy endpoint (eGFR chronic slope over 2 years) at the final analysis at 2-sided $\alpha = 0.05$. If the test is not significant, hypothesis testing stops. If the test is significant,

2. test the 3 secondary endpoints using a Bonferroni-Holm procedure to control for family-wise error rate at 2-sided $\alpha = 0.05$.

For the US, the hierarchy for the hypothesis testing will be as follows, if the test of the surrogate efficacy endpoint (UP/C response at Week 36) is significant:

1. test the primary efficacy endpoint (eGFR total slope over 2 years) at the final analysis at 2-sided $\alpha = 0.05$. If the test is not significant, hypothesis testing stops. If the test is significant,
2. test the efficacy endpoint of eGFR chronic slope over 2 years at the final analysis at 2-sided $\alpha = 0.05$. If the test is not significant, hypothesis testing stops. If the test is significant,
3. test the efficacy endpoint of change in eGFR from baseline of the double-blind period to 4 weeks post-cessation of randomized treatment at Week 112 at the final analysis at 2-sided $\alpha = 0.05$.

For planned statistical tests that are not formally performed as a result of the aforementioned multiplicity adjustment strategy, nominal 2-sided p-values (without adjustment for multiplicity) will be computed as a measure of the strength of association between the endpoint and the treatment effect rather than formal tests of hypothesis.

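### The patient random effect is redundant beside the unstructured covariance in the eGFR MMRMs; it can trigger an AR(1) fallback whose Week 108 test is too liberal if the effect is kept and patients differ in slope

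*SAP*

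**What the plan says.** SAP 8.7.1 describes the response as follows: "The dependent variable will be all available on-treatment natural log(eGFR) data from Week 2 to Week 108". After the fixed effects it adds: "In addition, patient will be included as a random effect". On covariance it says: "An unstructured covariance matrix will be assumed. If convergence issues arise, autoregressive-1 covariance structure will be used". The test is a difference of two visit effects: "Statistical significance of the treatment effect at Week 108 will be assessed by comparing with the treatment effect at Week 6".

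Protocol 12.7.3 includes the same patient effect and makes clear at which level the matrix applies: "An unstructured within-patient covariance structure will be assumed". The protocol synopsis repeats the combination. Neither document says whether the patient effect is removed under AR(1), what counts as a convergence issue, or whether any structure is tried before AR(1).

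The endpoint belongs to the non-US family in SAP 8.4, tested after the surrogate endpoint and the chronic slope are both significant: "test the 3 secondary endpoints using a Bonferroni-Holm procedure to control for family-wise error rate at 2-sided" α = 0.05. SAP 8.8.1.3 to 8.8.1.5, 8.8.2.2, 8.8.3 and 8.8.5 reuse the same MMRM, or one modelled on it, for exploratory endpoints.

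**The concern.** An unstructured matrix already contains any constant between-patient variance. A patient random effect on top of it adds a parameter that the data cannot separate. Software may set it to zero, report a singular information matrix, or fail to converge. The plan therefore contains a term that can do no good and can activate its own fallback.

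The fallback is the weak part. AR(1) plus a patient intercept has no term for patients declining at different rates, although the primary model in SAP 8.5.1.1 gives every patient random slopes. It also assigns the same correlation to neighbouring visits whether they are 2 or 12 weeks apart. The tested contrast spans Week 6 to Week 108, where slope differences accumulate. If the model understates the variance of that contrast, the p-value entering the Holm procedure is too small, and Holm cannot repair an invalid component p-value. Kenward-Roger does not correct a misspecified covariance.

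**Working it through.** **1. Redundancy.** SAP 4.1: "Study visits in the double-blind period will be conducted at 2, 4, 6, 8, and 12 weeks after randomization and at 12-week intervals thereafter". Weeks 2, 4, 6, 8, 12 are 5 visits; Weeks 24 to 108 in steps of 12 are 8; total 13. The unstructured matrix R has 13 × 14 / 2 = 91 parameters, and the patient variance τ² makes 92. The marginal covariance is V = R + τ²J, where J is the matrix of ones. Changing τ² to τ*² and R to R + (τ² − τ*²)J leaves V unchanged, so the rank is 91. The split between R and τ² is not identified. V, the Week 108 minus Week 6 contrast and its test are.

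**2. The plan's own figures.** Holm over three tests uses 0.05/3 = 0.0167, then 0.05/2 = 0.025, then 0.05, which keeps the family at 0.05 if each p-value is valid. No power, SD or error rate is given for this endpoint. The only slope SD usable here is 5.50 mL/min/1.73 m² per year for total slope (SAP 4.3.1.2). It reproduces the stated power of at least 90%: SE = 5.50 × √(2/150) = 0.635; 2.1/0.635 = 3.31; Φ(3.31 − 1.96) = 91.1%.

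**3. Assumptions for the log scale.** The documents give no log-scale variances, mean eGFR or dropout rate. I assume:
- mean eGFR 50 to 80, so log-scale slope SD from 5.50/80 = 0.07 to 5.50/50 = 0.11 per year;
- intercept SD 0.05 to 0.15, after baseline adjustment;
- residual SD 0.06 to 0.14;
- monotone dropout of 0% or 25% by Week 108.

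**4. Why slopes matter.** Take slope SD 0.09 and residual SD 0.10. Week 6 to Week 108 is 102/52 = 1.96 years. Slopes contribute (0.09 × 1.96)² = 0.031 to the variance of a patient's change; residuals contribute 2 × 0.10² = 0.020. About 61% of the variance comes from a source that the fallback does not model.

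**5. Type I error of the fallback.** The working structure (AR(1) by visit order) is fitted to the true random-intercept, random-slope covariance by minimising the expected Gaussian −2 log-likelihood. With r = model variance / true variance of the contrast, type I error = 2[1 − Φ(z × √r)], where z is the two-sided critical value. Example with slope SD 0.09, intercept SD 0.10, residual SD 0.10 and 25% dropout: r = 0.568; 1.96 × √0.568 = 1.477; type I error = 14.0%.

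| Covariance used | Nominal 5% | Nominal 1.67% |
|---|---|---|
| AR(1) with patient effect, slopes vary | 8.2-17.6% (median 12.9%) | 3.4-9.9% |
| AR(1) alone, slopes vary | 0.6-11.8% (median 4.5%) | 0.1-5.6% |
| AR(1) with patient effect, no slope variation (compound symmetry, or random intercept + AR(1)) | 5.0% | 1.7% |
| Unstructured alone (simulation at the example setting) | 5.0% | 1.5% |

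For AR(1) with the patient effect, the range is 8.2-15.2% without dropout and 8.6-17.6% with 25%. If 5.50 includes measurement error, true slope SD is smaller; a wider grid of slope SD 0.05 to 0.18 gives 6.8-19.5%.

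**6. Simulation check.** 600 trials, 150 per arm, at the example setting, with a large-sample reference distribution rather than Kenward-Roger: AR(1) with patient effect 13.2% (formula 14.0%), AR(1) alone 5.3% (formula 4.9%), unstructured alone 5.0%. Monte Carlo error near 5% is √(0.05 × 0.95/600) = 0.9 percentage points.

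**The case against.** The strongest reply is that the documents do not lead inevitably to a bad test. The software may set the redundant variance to zero, which leaves the ordinary unstructured MMRM with its error rate of about 5%. In a model labelled MMRM, naming patient as a random effect may be loose wording for the subject identifier of the repeated measures. The fallback sentence, "If convergence issues arise, autoregressive-1 covariance structure will be used", does not discuss the random effect; if an analyst dropped it, the error would be about 1-12% and often below nominal. The variance settings are assumptions. The endpoint is non-US only, comes late in the hierarchy and may be tested at 0.0167. The primary, surrogate and US analyses do not use this MMRM.

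All of that stands, and it limits the size of the point. It does not remove it. A programmer following both documents would code both terms, and nothing in either document removes the patient effect under AR(1). Random slopes are the sponsor's own assumption. Testing at 0.0167 does not help, since the error there is 3.4-9.9%, at least twice nominal.

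A reader might infer that the treatment effect itself is not identifiable. The documents do not support that: only the division of variance between two terms is undetermined.

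**Conclusion.** The point holds in conditional form. The patient effect is redundant as a matter of algebra. Three things must coincide for harm: the unstructured fit fails, the patient effect is kept under AR(1), and patients differ in slope. The plan as written implies the second, and the primary model assumes the third. The first is plausible; its probability was not estimated. When all three hold, type I error at nominal 5% is about 8-18% under the assumptions in step 3.

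A reader might infer that this is the error rate of the endpoint under the plan. It is not. If the planned model converges, the test is unaffected, and the range depends on variances and dropout that the documents do not give. The alpha consequence is confined to one of three non-US secondary endpoints. Because following the text literally can give a wrong test, this is more than a matter of missing detail and should be corrected before the final analysis.

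**What to change.** - Delete the patient random effect wherever an unstructured covariance is used: SAP 8.7.1 and the sections that refer to it, protocol 12.7.3 and the synopsis. If the protocol is left as it is, list the change in SAP 5.4, which at present declares one exception only.
- Define what counts as a convergence issue, including a singular information matrix.
- Replace AR(1) with a fallback that allows patient-specific slopes and unequal visit spacing, for example random intercept and slope with a spatial-power residual. Alternatively, use sandwich standard errors under the fallback, with a named degrees-of-freedom method; these would replace Kenward-Roger inference in that case only. Heterogeneous Toeplitz is not a full answer, because it also indexes correlation by visit order.

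The example fallback covers the random-slope truth used above, but its error rate was not computed here; a short simulation on blinded data would settle the choice. The cost is a few sentences in two documents, with no new data and no change to the endpoint or the planned unstructured model.
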